Cover Page

ID: 5160230

Benefit of Adding Stretching to Standard
Intervention for Patients with
Nonspecific Mechanical Neck Pain

NCT03194490

Date: October 09, 2019

Methods

Participants

Forty-three participants who had at least two weeks of non-specific mechanical neck pain were randomly assigned to either the combined intervention (passive cervical mobilization, active range of motion exercises, and stretching techniques) ($n_1=20$) or standard intervention group (passive cervical mobilization and active range of motion exercises) ($n_2=23$). At two-weeks follow-up, 2 participants dropped out of the study due to health conditions, and at 8 weeks, 3 participants withdrew. (Refer to Figure 1) Thus, 38 participants with a mean age 31.0 ± 8.3 years, height 1.6 ± 0.1 m, mass 72.8 ± 17.5 kg, and body mass index 26.9 ± 6.7 kg/m² completed this study. All participants read and signed a consent form that was approved by the institutional review board at Loma Linda University. This study was registered in ClinicalTrials.gov with Protocol #5160230. The participants met the following inclusion criteria: between 18 and 60 years of age, had non-specific neck pain for at least 2 weeks, and pain intensity of more than 2 points on a numeric pain rating scale (NPRS) in the past week. Participants were excluded from the study if they had one or more of the following conditions: specific diagnosis of the cervical spine, such as spinal stenosis, disc prolapse, previous surgery in the neck and shoulder areas, shoulder pathology (bursitis, tendonitis, adhesive capsulitis), history of severe trauma, ligamentous instability, hypermobility syndrome, migraine (frequency more than twice per month), spasmodic torticollis, radiculopathy due to peripheral nerve entrapment, fibromyalgia, severe psychiatric illness, inflammatory rheumatic diseases, pregnancy or other on-going therapies.

The identification of the study's excluding criteria was conducted through clinical examination, medical history and self-reported questionnaires ⁶. Participants were randomly assigned to either the combined intervention group or the standard intervention group using a random number table. Demographic and general characteristics of the participants are presented in **Table 1**.

Instrumentation

Cervical ROM

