The cervical mobilization and stretching exercise techniques were performed by a licensed physical therapist who has 6 years of experience in manual physical therapy.

Self-administered stretching exercises were performed by participants in the combined intervention group to the following muscles: the extensor muscles, the upper part of the trapezius, and the posterior scalene ⁶. Each movement was held for 30 seconds and repeated 3 times. Lastly, the participant was instructed to perform a neck straightening exercise by retracting the neck (Chin tuck) 5 times for 3-5 seconds. Subjects in the combined intervention group were provided with written instruction of the stretching exercises and directed to perform stretching exercise 5 times a week, each exercise session takes about 10 minutes. Patients were also instructed to keep a stretching diary to track their stretch exercise frequency.

Data collection:

Data was collected at baseline, one week after intervention, and week 4. The final data collection date was set at week 8 as a follow up to determine whether the participant was able to maintain gains at one month following the interventions.

Statistical Analyses

A sample size of 50 participants was estimated using a moderate effect size of 0.25, level of significance 0.05, and power of 0.80. Data was summarized using mean and standard deviation ¹ for quantitative variables and counts (%) for qualitative variables. The normality of continuous variables was examined using Shapiro Wilk's test. The distribution of the participants' characteristics by study group were evaluated using chi-square for qualitative variables and independent t- test for quantitative variables. Mixed factorial analysis of variance (ANOVA) was used to examine changes in cervical ROM variables, pressure pain threshold, NPRS, GROC, and NDI scores by study group over time. Post hoc comparisons using Bonferroni test and effect size were computed to identify significant differences over time. We compared percent change (4 weeks vs. baseline) for all outcome variables between the two study groups using independent t- test and Mann- Whitney test. To examine whether there were any changes in the outcome variables at 4 weeks follow up paired t- test was used. The level of significance was set at $p \leq 0.05$. Statistical analysis was performed using IBM SPSS Software version 24 for Windows (Chicago, IL, USA).

Results

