Thirty-eight (38) subjects with a mean \pm SD age 30.9 ± 8.1 years and body mass index (BMI) 26.8 ± 6.7 kg/m² participated in the study. Sixty- five percent of the participants were females (n=

26). There was no significant difference between the two study groups in terms of age, Body Mass Index (BMI), cervical ROM and pressure pain threshold at baseline. Demographic and general characteristics are presented in **Table 1**.

Changes in ROM

Results of the mixed factorial ANOVA for ROM is displayed in **Table 2**. There was a significant difference in mean ROM during extension over time ($F_{2,72}=6.8$, $p=0.002$, $\eta^2=0.20$), and a significant group by time interaction ($F_{2,72}=3.6$, $p=0.02$). Bonferroni post hoc comparison revealed that the difference was significant between baseline and one week later (70.2 ± 2.1 vs. 74.3 ± 2.4 , $p=0.04$), baseline and 4 weeks later (70.2 ± 2.1 vs. 76.6 ± 2.0 , $p=0.001$), however, there was no significant difference between one week later and 4 weeks ($p=0.15$). In addition, the % improvement from baseline to 4 weeks later was significantly different between the combined intervention and standard intervention groups respectively (18.9% vs. 3.0% ; $t=2.4$, $p=0.02$). (Refer to **Table 2**)

Also, there was a significant difference in mean ROM during right lateral flexion over time ($F_{2,72}=13.8$, $p<0.001$, $\eta^2=0.30$), and a significant group by time interaction ($F_{2,72}=2.9$, $p=0.04$). Bonferroni post hoc comparison revealed that the difference was significant between baseline and one week later (40.8 ± 1.5 vs. 43.8 ± 1.3 , $p=0.03$), baseline and 4 weeks later (40.8 ± 1.5 vs. 46.8 ± 1.4 , $p<0.001$), and between one week later and 4 weeks (43.8 ± 1.3 vs. 46.8 ± 1.4 , $p=0.001$). In addition, the % improvement from baseline to 4 weeks later was significantly different between the combined intervention and groups respectively (23.2% vs. 10.8% ; $t=1.8$, $p=0.04$). (Refer to **Table 2**).

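### Eleven outcomes are tested at 0.05 with no primary outcome named and no correction across outcomes, and the three ROM interactions called significant disagree with their own printed F and df

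*Combined protocol and SAP*

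**What the plan says.** - **Model.** Statistical Analyses: "Mixed factorial analysis of variance (ANOVA) was used to examine changes in cervical ROM variables, pressure pain threshold, NPRS, GROC, and NDI scores", by group over time, at a significance level of 0.05.
- **Second between-group comparison.** Percent change from baseline to week 4 is compared "between the two study groups using independent t- test and Mann- Whitney test".
- **Multiplicity.** The only correction is this: "Post hoc comparisons using Bonferroni test and effect size were computed to identify significant differences over time". It concerns visits within an outcome, not the set of outcomes.
- **Sample size.** "A sample size of 50 participants was estimated using a moderate effect size of 0.25, level of significance 0.05, and power of 0.80". No outcome is attached to it.
- **Primary outcome.** None is named. The Participants section says "This study was registered in ClinicalTrials.gov with Protocol #5160230"; the registration was not available for this review.
- **Visits.** Baseline, week 1 and week 4, and then: "The final data collection date was set at week 8 as a follow up".
- **Results.** Three of the six ROM directions (extension, right and left lateral flexion) are reported with significant group-by-time interactions. The other eight outcomes are reported as not differing between groups. For extension the text gives a "significant group by time interaction ($F_{2,72}=3.6$, $p=0.02"

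**The concern.** The trial asks whether adding stretching helps. The only between-group benefits in the text are these three ROM interactions and the matching percent-change tests. Two things weaken them.

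First, 0.05 is the error rate of each test, not of the set of 11, and no primary outcome in this document says which result carries the conclusion.

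Second, the printed p-values do not follow from the printed F and df. A reader could take three significant interactions as evidence of added benefit, although two of them exceed 0.05 on their own printed statistics.

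**Working it through.** **Inputs.** The outcomes are six ROM directions (Instrumentation), pressure pain threshold (PPT) right and left, NPRS, GROC and NDI: 6 + 2 + 1 + 1 + 1 = 11. There are 38 completers (18 + 20). With two groups and three visits, the error df are (38 − 2) × (3 − 1) = 72, as printed.

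**1. p from the printed F.** With 2 numerator df, the upper tail is p = (1 + 2F/72)^(−36) = (1 + F/36)^(−36). The 5% critical value is F = 3.12.

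The formula first reproduces other printed values:
- extension time effect, 6.8: 0.002 (printed 0.002)
- right PPT time effect, 4.3: 0.017 (0.02)
- right PPT interaction, 0.98: 0.38 (0.38)
- NPRS interaction, 1.5: 0.23 (0.23)
- NDI interaction, 2.8: 0.067 (0.07)

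The interactions called significant:

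| Outcome | Printed F(2,72) | Printed p | p from F | Range for rounding of F (±0.05) | F needed for printed p |
|---|---|---|---|---|---|
| Extension | 3.6 | 0.02 | 0.032 | 0.031–0.034 | 4.13 |
| Right lateral flexion | 2.9 | 0.04 | 0.061 | 0.059–0.064 | 3.37 |
| Left lateral flexion | 3.0 | 0.03 | 0.056 | 0.053–0.059 | 3.68 |

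Rounding does not close the gap. A sphericity correction widens it: at an assumed epsilon of 0.8 the values are 0.043, 0.074 and 0.069.

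**2. Were four visits analysed?** F(3,108) gives 0.016, 0.038 and 0.034, which round to the printed p-values. But on those df the extension time effect would be 0.0003, the right PPT time effect 0.007 and the NDI interaction 0.043. Their printed p-values fit F(2,72) only. The text also reports post hoc comparisons among at most three visits and gives the follow-up its own paired t-test. The source of the error therefore stays open.

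**3. Other inconsistencies.**
- The left lateral flexion time effect repeats its interaction's F = 3.0 and p = 0.03. Partial eta-squared is then F/(F + 36) = 3/39 = 0.08, yet 0.30 is printed, beside a post hoc p below 0.001.
- The PPT group effects are printed as F(2,72) = 0.02 with p = 0.90 (right) and 0.86 (left). On (2,72) p is 0.98. On (1,36) it is 0.89, or 0.875–0.903 allowing for rounding of F, so 0.90 fits and 0.86 does not.

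**4. Percent change, 18 + 20 − 2 = 36 df.**
- Extension: t = 2.4, two-sided 0.022 (printed 0.02).
- Right lateral flexion: t = 1.8, two-sided 0.080, one-sided 0.040 (printed 0.04).
- Left lateral flexion: t = 2.1, two-sided 0.043, one-sided 0.021 (printed 0.02).

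The lateral flexion values match one-sided t-tests, or may come from the Mann-Whitney test. The document states neither.

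**5. Multiplicity.** The chance of at least one false positive in 11 independent tests is 1 − 0.95^11 = 0.43. By simulation it is about 0.30 and 0.22 at assumed common correlations of 0.5 and 0.7.

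Holm at the printed p-values:
- Across 11: extension 0.02 × 11 = 0.22; left lateral flexion 0.03 × 10 = 0.30; right lateral flexion 0.04 × 9 = 0.36.
- Across the six ROM directions: 0.02 × 6 = 0.12; 0.03 × 5 = 0.15; 0.04 × 4 = 0.16.

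From the printed F, extension becomes 0.0323 × 11 = 0.36 across 11 and 0.0323 × 6 = 0.19 across six. Both lateral flexions exceed 0.5 across 11.

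Holm ignores correlation. A max-statistic adjustment of extension at its printed p = 0.02, for assumed correlations of 0.5, 0.7 and 0.9, gives 0.09–0.10, 0.07–0.08 and about 0.05 across six. Across 11 it gives 0.14–0.15, 0.10–0.11 and about 0.06.

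**The case against.** The strongest reply is that the text overclaims little. It has no conclusion section, reports the eight other outcomes as non-significant, and closes by saying that no outcome changed significantly by group after the follow-up. A primary outcome may be registered, and Table 2, which is not in the supplied text, may hold the missing raw values. All of this is fair, and it keeps the point to one of reporting and interpretation.

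Three or more hits in 11 is also unlikely under a global null: 1.5% if independent, about 7% at an assumed correlation of 0.7. So it would be wrong to call these chance findings. But that count takes the printed p-values as correct; at the printed F and df there is one hit.

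Holm across 11 correlated outcomes is conservative, and any family chosen now is chosen after the data are known. That stands: extension could be borderline within a six-ROM family at very high correlation. If F(3,108) proved right (p = 0.016), it would fall to about 0.04 there at an assumed correlation of 0.9.

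Some printed eta-squared values for other outcomes (0.20, 0.30, 0.60) differ from F/(F + 36) only as one-decimal rounding would, so they are not evidence of error. The left lateral flexion line is not explained that way.

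**Conclusion.** The concern holds. All three interactions reported as significant have p-values that do not follow from their F and df. At the printed F and df, only extension (0.032) is below 0.05, while right (0.061) and left (0.056) lateral flexion are not. Which printed quantity is wrong cannot be settled from the document, so the lateral flexion results should not be declared non-significant before the output is checked.

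Separately, nothing controls error across the 11 between-group tests. On the printed p-values no result survives adjustment across 11, either by Holm or by the correlation-aware calculation up to an assumed correlation of 0.9. The absence of a primary outcome is established for this document only. The arithmetic on F, df and p needs no assumption beyond the printed numbers; the correlation figures rest on assumed values.

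**What to change.** 1. Check the statistical output and correct F, df and p for the three ROM interactions, the repeated left lateral flexion line and the PPT group effects. State how many visits each ANOVA used, and the test and sidedness behind each percent-change p-value.
2. Check the registration. If it names a primary outcome, base the conclusion on it. If not, say that none was named and do not choose one now.
3. Use the group-by-time test as the single test of added stretching for each outcome. Report raw and Holm-adjusted p-values for all 11, show the six-ROM family alongside, and keep percent change as supportive. GROC is reported only from week 1, so percent change from baseline can cover at most 10 outcomes.
4. Unless a reconciled result is the registered primary outcome or survives adjustment, label the extension and lateral flexion findings exploratory.

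Suggested wording, conditional on the reconciled values and on no registered primary outcome:

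> After Holm adjustment across 11 outcomes, an added benefit of stretching was [was not] demonstrated; unadjusted ROM results are exploratory. Non-significant differences in pain and disability, with 38 completers of 50 planned, do not show absence of effect.

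The cost is a check of the output and registration, a short recalculation and revised wording, with no new data. The ROM findings may become exploratory, and adjustment lowers power per outcome in an already small sample. Because the family is chosen after the results are known, the raw values must stay visible.

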The study was conducted over 8 weeks. Participants were randomly allocated into two groups: *combined intervention* (passive cervical mobilization, active range of motion exercises, and stretching techniques) ($n_1=18$) and *standard intervention groups* ($n_2=20$). The randomization was performed by a person who was blind to the patient's allocation. Participants in the *combined intervention group* received 30 minutes of passive manual therapy consists of (i) cervical mobilization and (ii) active cervical range of motion exercises to be performed at home 3-4 times daily, (iii) stretching techniques for 2 sessions per week for 4 weeks (iv) a self-administered stretching exercises to be performed at home 5 times a week. Participants in *standard intervention group* received 15 minutes of manual therapy consists of (i) cervical mobilization and (ii) active range of motion exercises to be performed at home 3-4 times daily.

Cervical Mobilization techniques were used in the study and consisted of low-velocity non-thrust cervical joint mobilizations for unilateral symptoms: postero-anterior unilateral vertebral pressure, traction, and transfer vertebral pressure. For bilateral symptoms, the following joint mobilization were applied: postero-anterior central vertebral pressure, postero-anterior unilateral vertebral pressure (2 sides), longitudinal movement, traction and rotation. These techniques have been described previously by Anandacoomarasamy, Barnsley³¹. Both groups received 10 minutes of cervical mobilization for 2 sessions per week for 4 weeks.

Active Cervical Range of Motion Exercises (ACROM) were performed 10 repetitions 3–4 times daily. The ACROM exercise consisted of the subject placing four fingers over the manubrium bone and placing chin on the fingers. The subject was then instructed to rotate to one side as far as possible and return to neutral and then actively rotate to the other side³². Both groups performed ACROM exercises. Subjects were advised to maintain their usual activity within the limits of pain.

Stretching techniques were performed in the combined intervention group for 30 seconds for each muscle and repeated 3 times twice a week to the following muscles: anterior, middle and posterior scalene, upper fibers of trapezius, pectoralis minor muscles and interspinous muscles as described by Ylinen, Chaitow, Nurmenniemi, Hill ³³.

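### The mixed ANOVA has no sphericity check or correction; for right lateral flexion the uncorrected test is modestly anti-conservative, and the printed F, df and p for the range-of-motion interactions must be reconciled as well

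*Combined protocol and SAP*

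**What the plan says.** Statistical Analyses states: "Mixed factorial analysis of variance (ANOVA) was used to examine changes in cervical ROM variables". The same model is applied to the other outcomes, with study group and time as its factors. The threshold is given as "The level of significance was set at $p \leq 0.05". The section names one assumption check, the Shapiro-Wilk test of normality. It mentions neither a test of sphericity nor an adjustment of the degrees of freedom.

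Under Data collection, the visits are baseline, one week, week 4 and a follow-up at week 8. The Results print the range-of-motion (ROM) interactions on 2,72 df, which corresponds to three visits and the 38 completers (18 and 20 under Procedures). Three of these interactions are called significant: extension (F=3.6, p=0.02), right lateral flexion ("a significant group by time interaction ($F_{2,72}=2.9$, $p=0.04") and left lateral flexion (F=3.0, p=0.03). The interactions for pressure pain threshold, NPRS, GROC and NDI are reported as not significant.

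**The concern.** With three visits, the univariate F test of group by time has its nominal size only if the three pairwise visit differences have equal variance. Visits at 0, 1 and 4 weeks give little reason to expect that, since nearby visits tend to be more alike than distant ones. When the condition fails, the test on full df rejects too often.

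The right lateral flexion figures point to failure directly. Baseline to one week is a change of 3.0 degrees with p=0.03. The next interval is also 3.0 degrees, but far more precise: "between one week later and 4 weeks (43.8 ± 1.3 vs. 46.8 ± 1.4 , $p=0.001". Equal differences with such different p-values need unequal variances.

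The three ROM interactions carry the statement that stretching adds benefit, and their printed p-values lie between 0.02 and 0.04, so the choice of df row matters.

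**Working it through.** **1. The printed p-values at the printed df.** With 2 numerator df the upper tail is exact: p = (1 + 2F/72)^(-36).

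| Interaction | F | p on 2,72 | p on 3,108 | Printed p |
|---|---|---|---|---|
| Extension | 3.6 | 0.032 | 0.016 | 0.02 |
| Right lateral flexion | 2.9 | 0.061 | 0.038 | 0.04 |
| Left lateral flexion | 3.0 | 0.056 | 0.034 | 0.03 |

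Rounding of F (2.85 to 2.95) gives 0.059 to 0.064 for right lateral flexion. The 5% critical value on 2,72 df is 3.12. No printed p is reproduced on 2,72. All three are reproduced on 3,108, the df for 38 people and four visits: 4-1=3 and 36×3=108.

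**2. Difference variances for right lateral flexion.** Inputs from Changes in ROM: means 40.8, 43.8, 46.8; time F=13.8; post hoc p=0.03 and 0.001; N=38.

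- Time mean square = 38 × (3² + 0² + 3²)/2 = 342. Error mean square = 342/13.8 = 24.8.
- The three squared standard errors of difference sum to 6 × 24.8/38 = 3.91.
- Bonferroni p=0.03 means t(36)=2.72, so SE = 3.0/2.72 = 1.10. Bonferroni p=0.001 means t=3.97, so SE = 3.0/3.97 = 0.76.
- The remainder gives SE=1.46 for baseline to 4 weeks. Then t = 6.0/1.46 = 4.12 and Bonferroni p=0.0006, which agrees with the printed p<0.001.
- Multiplying the squared SEs by 38 gives variances of about 46, 22 and 81.

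**3. Epsilon.** Let T be the sum of the three variances divided by 3, and P = [2 × (sum of pairwise products) - (sum of squares)]/12. Then epsilon = T²/[2(T² - 2P)]. Here T=49.6 and P=322, so epsilon = 2457/[2 × (2457 - 643)] = 0.68 (0.62 to 0.72 over rounding of the inputs). Mauchly's W = P/(T/2)² = 0.52, which a routine check would have flagged.

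If the post hoc p-values are unadjusted, the squared SEs are 1.76, 0.70 and 1.45, and epsilon is 0.81.

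**4. Size of the uncorrected test.** Simulating under no interaction with these variances and 36 error df per contrast, the nominal 5% test rejects in about 6.8% of draws at epsilon 0.68 (6.5 to 7.3% over rounding) and about 5.9% at 0.81. With the Greenhouse-Geisser correction it is about 5% in both cases.

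**5. Corrected p-values at the printed F**, from the upper tail of F on 2×epsilon and 72×epsilon df:

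- Right lateral flexion: 0.083 at epsilon 0.68 (0.080 to 0.088 for epsilon 0.72 to 0.62); 0.073 at 0.81.
- Extension: the three printed post hoc p-values (0.04, 0.15, 0.001, read as Bonferroni) give SEs of 1.58, 1.13 and 1.61, epsilon 0.86 (0.82 to 0.92) and p=0.039 (0.037 to 0.042). These SEs imply a time F of 399.4/[38 × (1.58² + 1.13² + 1.61²)/6], about 9.9, against the printed 6.8. Read as unadjusted, the SEs are 1.92, 1.56 and 1.79, the implied time F is about 6.75, epsilon is 0.95 and p is about 0.035. Extension would reach 0.05 only at epsilon of about 0.70.
- Left lateral flexion: the time F is printed as 3.0, the same as the interaction F, which does not fit its printed eta-squared of 0.30. If time F is taken as 36 × 0.30/0.70 = 15.4, epsilon is about 0.78 and p=0.070. This rests on that assumption.

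**The case against.** The strongest reply is that sphericity is not what makes right lateral flexion unsafe. At the printed F and uncorrected df it already misses 0.05, and the correction only moves it from 0.061 to 0.083. That is right, and it limits the point.

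A reader might infer that the correction itself carries the result across 0.05. One can get there by taking p=0.04 as correct and solving back for F of about 3.37; the corrected p is then 0.060 at epsilon 0.68 and 0.051 at 0.81 (0.045 to 0.056 over rounding). But that discards the printed F=2.9, and the documents give no reason to trust the p over the F.

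Second, the 2,72 label is not firm evidence that every p-value is uncorrected. The left pressure pain threshold interaction (F=0.48) gives p=0.62 on 2,72; the printed 0.59 fits an epsilon of about 0.81 to 0.89. The between-group effects for that outcome family also carry 2,72, though F=0.02 there gives 0.98, while 1,36 df gives 0.89, close to the printed 0.90 and 0.86. Right pressure pain threshold, NPRS and NDI interactions do fit uncorrected 2,72. So a reader should not conclude that uncorrected p-values were used throughout.

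Third, if the ROM interactions were four-visit tests, the three-visit epsilon is not the relevant one. Right lateral flexion would then be 0.038 uncorrected and would pass 0.05 once epsilon fell below about 0.81. The correction could be decisive, but the four-visit epsilon cannot be derived from the text.

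None of this removes the gap: whoever reconciles these rows must choose a df rule, and the plan gives none.

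**Conclusion.** The point holds in limited form. The plan has no sphericity check or correction. For right lateral flexion the printed figures imply epsilon of about 0.68, or 0.81 on the unadjusted reading, and an uncorrected interaction test with a true size of about 6-7%. This assumes a three-visit model and that the printed means, time F and post hoc p-values belong together.

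Right and left lateral flexion are not significant at their printed F and df even without correction (0.061 and 0.056). Extension stays below 0.05 at its derived epsilon, on either reading of its post hoc p-values, although on the Bonferroni reading those p-values do not agree with its printed time F.

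It would go too far to say that all the group-by-time tests are undermined. The interactions reported as not significant are not threatened, because a correction can only raise their p-values. The larger uncertainty is which F, df and number of visits belong to each ROM result.

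**What to change.** In Statistical Analyses:

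- State that all within-subject tests with three or more visits, both time and group by time, use Greenhouse-Geisser corrected df and p-values.
- State how many visits enter each model, and in particular whether week 8 is included.

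In Results, reprint F, df, epsilon and p for every outcome from that one row so that they agree with each other. Keep a ROM interaction claim only where the corrected p is at or below 0.05. Adding the correction without this reconciliation would leave the present contradictions in place.

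The cost is a short addition to the plan and a reprint from an analysis already run, or a re-run if the corrected row was not kept. The downside is slightly larger p-values.
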